Patients who meet the inclusion criteria and agree to participate in the study will undergo a thorough clinical low back examination according to standard routine, and assessment of function and physical capacity performed by an experienced physiotherapist.

Before start, the patient will undergo MRI examination (NÄL, Trollhättan, Sweden) and functional imaging methods without contrast agents (such as diffusion tensor imaging (DTI), DIXON³, magnetic resonance spectroscopy (MRS) and T2 mapping⁴) will be obtained.

Sample size calculation regarding the training intervention: based on a p-value 0.05, power 0.85, SD 0.1 and a minimal clinical change in Visual Analog Scale (VAS)/pain 0.11 (Hawker et al-11) gives 23 people/group.

Sample size calculation regarding MRI: is based on the possibility of detecting a 0.5% difference (power size 0.041) regarding the T2 value between the three occasions with significance level 0.05 and power 0.8. Considering possible dropouts, we expect 30 patients in each group, a total of 90 patients.

Intervention

Training intervention

After completing the clinical low back examination, the patient will initially be randomized to either group 1 & 3, then 2 & 3 (see below). As more units will be included over time (Vänersborg/Trollhättan/Uddevalla, Sweden), we expect several training groups on-going at the same time.

Group 1 Aerobic

Group 2 Core stability

Group 3 Daily Physical Activity

Group 1 & 2 will be training according to the following program for 3 months: 45 minutes 3 times/week, 2 times digitally supervised by experienced physiotherapist and one-time un-supervised training. Then 3 months of un-supervised training with regular follow-up meetings with responsible physiotherapist.

Each training session includes warm-up, specific exercises with the ability adjust according to pain and function, and progression, then final relaxation exercises. Estimated number of participants/group (1&2): 10-12, inclusion rate about 35 patients first year, 35 patients 2nd year and 20 patients 3rd year (only preliminary calculation as we depend on the inclusion rate of patients and number of involved health care centre).

Group 3 (~10 patients will run concurrently with group 1or 2) will receive training instruction regarding daily physical activity equivalent to >150 min/week according to WHO recommendations (7) (11) (12) for 6 months. The activity will be recorded in a health app on the patient's mobile.

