The MR images will be assessed according to clinical routine and in addition, when relevant, according to conventional classification systems for specific morphological changes such as Modic Types, Schmorls nodules, High-Intensity Zones. New objective tissue characteristic measures (histogram analysis, shape/texture analysis and regional analysis) in vertebrae/disc/muscle will be extracted by the software we previously have developed and validated based on artificial intelligence (histogram analysis, shape/texture analysis and regional analysis) (30)

Data analysis

All data will be documented in a separate database. This database will be password protected and only those directly involved in the study will have access to the database. In addition, all personal data will be pseudonymised according to EU general data protection rules (GDPR) before exported into SPSS (<https://www.ibm.com/products/spss-statistics>). Data will only be analysed at the group level.

The questionnaires in Webropol will be exported to SPSS for analysis.

Descriptive statistics will be presented as mean/standard deviation or median/range. Comparisons between and within groups will be conducted using either parametric or non-parametric statistical methods depending on data quality. Bonferroni correction will be performed when multiple comparisons are done. All statistical tests will be 2-tailed with statistical significance level of $p < 0.05$.

Spearman rank correlation will be used analysing the association between specific morphological changes and clinical data. In addition, multiparametric prediction modelling will be performed (based on unsupervised/supervised machine-learning).

Expected result / Clinical relevance

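### The two supervised arms are delivered in classes of 10-12 and the third is not, but neither the sizing nor the named group comparisons allow for class

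*Protocol*

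**What the plan says.** Under Intervention (Training intervention), the protocol plans supervised classes for Groups 1 and 2: "Estimated number of participants/group (1&2): 10-12". For the first 3 months the weekly sessions are "2 times digitally supervised by experienced physiotherapist and one-time un-supervised training". It adds that "we expect several training groups on-going at the same time". Group 3 receives instruction on daily activity and logs it in a phone app. About 10 Group 3 patients run alongside each Group 1 or Group 2 intake, but no class is described for them. Patients in all three groups can book video appointments with the responsible physiotherapist.

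Under Method & Materials, the training sample size is "based on a p-value 0.05, power 0.85, SD 0.1 and a minimal clinical change in Visual Analog Scale (VAS)/pain 0.11", which "gives 23 people/group". Enrolment is then set: "Considering possible dropouts, we expect 30 patients in each group, a total of 90 patients". No ICC, design effect or class size enters the calculation.

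Under Data analysis: "Comparisons between and within groups will be conducted using either parametric or non-parametric statistical methods depending on data quality", with Bonferroni correction for multiple comparisons and two-sided testing at 0.05. Class and physiotherapist appear neither there nor among the items listed under Data collection.

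**The concern.** Patients who train together twice a week for 3 months share sessions, fellow participants and an instructor's style. Their outcomes may therefore be more alike than those of patients who train alone. When such clustering exists in two arms and not in the third, a test that counts every patient as independent treats class-to-class variation as if it were patient-to-patient variation.

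Hypothesis 1 contrasts the supervised arms with daily activity, so one side of that contrast is clustered. The protocol also asks whether all three groups differ, and in aerobic versus core both sides are clustered. With so few classes, one unusually cohesive class or effective instructor could pass for an effect of exercise type. Allocation is also described as first between Groups 1 and 3 and then between Groups 2 and 3, so aerobic and core classes may fall in different calendar periods. If class membership is not recorded, no later analysis can address any of this.

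**Working it through.** **The plan's own figure.** Inputs from Method & Materials: difference 0.11, SD 0.1 (so 1.1 SD), alpha 0.05 two-sided, power 0.85. The two-group formula gives n = 2(1.96 + 1.036)² / 1.1² = 14.8, i.e. 15 per group, or 16 with a t-test. The stated 23 does not follow from these inputs, which is a separate point. What matters here is that the calculation contains no clustering term.

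**Number of classes.** At 30 per arm, 30/12 = 2.5 to 30/10 = 3 classes. At 23 per arm, 23/12 = 1.9 to 23/10 = 2.3.

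**Formulas.** With class size m, ICC ρ and total SD held fixed, the design effect is DE = 1 + (m − 1)ρ. The true standard error divided by the naive one is:
- supervised versus daily activity (one arm clustered): √((DE + 1)/2);
- aerobic versus core (both arms clustered): √DE.

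The true type I error of a nominal 5% test is 2(1 − Φ(1.96/ratio)). The values of ρ are assumptions; m = 10 to 12 is the protocol's.

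| Assumed ρ | DE | SE ratio, supervised vs daily | Type I error | SE ratio, aerobic vs core | Type I error |
|---|---|---|---|---|---|
| 0.01 | 1.09-1.11 | 1.02-1.03 | 5.5-5.6% | 1.04-1.05 | 6.0-6.3% |
| 0.05 | 1.45-1.55 | 1.11-1.13 | 7.7-8.3% | 1.20-1.24 | 10.4-11.5% |
| 0.10 | 1.90-2.10 | 1.20-1.24 | 10.4-11.5% | 1.38-1.45 | 15.5-17.6% |

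**If part of the effect is shared with the concurrent Group 3 batch.** Suppose half of ρ (an assumption) is common to a class and the Group 3 patients running alongside it. That half cancels in the contrast. With n = 30 and m = 10, the squared SE ratio is [10(ρ/2) + (1 − ρ) + (1 − ρ/2)]/2 = 1 + 1.75ρ. At ρ = 0.01, 0.05 and 0.10 the type I error is then 5.2%, 6.0% and 7.1%.

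**Power on the stated inputs.** Power = Φ(1.1·√(23/2)/ratio − 1.96).
- No clustering: Φ(3.73 − 1.96) = 0.96.
- Supervised versus daily: about 0.95 at ρ = 0.01, 0.91-0.92 at 0.05 and 0.85-0.87 at 0.10.
- Aerobic versus core: about 0.94-0.95, 0.85-0.87 and 0.73-0.77.

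**Small number of classes.** Three classes in each of two arms leave 3 + 3 − 2 = 4 between-class degrees of freedom for aerobic versus core. The critical value is 2.78 instead of 1.96, so an interval is about 2.78/1.96 = 1.42 times as wide before any widening from ρ itself. The normal-approximation figures above are optimistic for the same reason.

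**The case against.** Several stronger readings are tempting, and the document does not support them.

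- **That each class has a single physiotherapist.** The text says only that sessions are supervised by an experienced physiotherapist. One therapist may lead every class, or several may share one. Shared classes are enough for the point.
- **That the planned tests are fixed as assuming independence.** The protocol speaks only of parametric or non-parametric comparisons. A mixed model is parametric and is not excluded, and a class term could stand in an SAP that is not at hand. What can be said is that the sizing has no allowance and the named comparisons mention none.
- **That the standard errors are too small.** This depends on an ICC that the protocol does not give. At 0.01 the effect on the Hypothesis 1 contrast is slight.
- **That Group 3 patients are wholly independent.** They start in batches alongside the classes and can book the responsible physiotherapist, so period effects and some therapist effects may be shared and cancel. The type I errors for supervised versus daily activity are therefore upper figures for each assumed ICC.
- **That the trial is underpowered because of clustering.** On the stated 1.1 SD at alpha 0.05, 23 per group keeps the planned 0.85 for supervised versus daily activity up to an ICC of about 0.10-0.12. The limit is lower for aerobic versus core (about 0.05-0.06), and for supervised versus daily activity if Bonferroni were applied at 0.05/3 (about 0.03-0.04). The protocol does not give the number of comparisons.

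It is also fair that the largest errors belong to aerobic versus core, which Hypothesis 1 does not cover, and that a class variance from about three classes per arm is barely estimable. These objections limit the claim. They leave standing the partially nested design, the absence of any clustering allowance in the sizing, and the lack of any provision to record class.

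**Conclusion.** The point holds in conditional form. Groups 1 and 2 are clustered by delivery, with about three classes per arm; no class is described for Group 3; and neither the sizing nor the named comparisons allow for it. Any positive class ICC not offset by effects shared with the concurrent Group 3 batch makes patient-level error bars too narrow.

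Over an assumed ICC range of 0.01 to 0.10, the true type I error rises from about 5.5% to at most 10-12% for supervised versus daily activity, and from about 6% to 16-18% for aerobic versus core. The harm is false-positive findings and over-narrow intervals. A shortage of patients for the Hypothesis 1 contrast does not follow from the protocol's inputs at alpha 0.05. More patients in the same few classes would not fully cure the problem.

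**What to change.** - Record the training class, leading physiotherapist and concurrent cohort for every patient, including the Group 3 batch.
- Alongside the simple group comparison, pre-state a class-adjusted sensitivity analysis: a mixed model with a random class effect in the supervised arms only, cohort as a factor where estimable, and small-sample degrees of freedom (Kenward-Roger or Satterthwaite). Report the estimated ICC.
- State in the sample-size paragraph that the 23 per group assumes no clustering.
- Say in advance that aerobic versus core will be interpreted cautiously, because class and possibly calendar period are hard to separate from exercise type.

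The cost is about three recorded variables and one further model. The downside is wider intervals, markedly so for aerobic versus core with about 4 between-class degrees of freedom, and an imprecise class variance. That imprecision is why the adjusted model should sit beside the simple comparison and not replace it.

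### The pairing scheme in the protocol, read plainly, gives about 23/23/44 of 90 patients rather than the expected 30 per group, and no allocation ratio is stated to reconcile the two

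*Protocol*

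**What the plan says.** All the relevant text is in the Protocol, in the sample size paragraphs of Method & Materials and under Intervention, Training intervention.

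- Target sizes: "Considering possible dropouts, we expect 30 patients in each group, a total of 90 patients".
- Randomisation: "the patient will initially be randomized to either group 1 & 3, then 2 & 3". No ratio is given for either pairing.
- Supervised class size: "Estimated number of participants/group (1&2): 10-12".
- Comparator: "Group 3 (~10 patients will run concurrently with group 1or 2".
- Parallel running, given as a consequence of more units joining over time: "we expect several training groups on-going at the same time".
- Accrual: "inclusion rate about 35 patients first year, 35 patients 2nd year and 20 patients 3rd year". The protocol calls this a preliminary calculation.

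The clinical sample size calculation gives 23 per group. The protocol moves to 30 for dropouts without stating a dropout rate.

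**The concern.** Group 3 appears in both pairings and each supervised group in only one. If a class of 10-12 is matched by about 10 Group 3 patients, Group 3 gains about one patient for every supervised patient, and the supervised patients are then divided between two arms. Over the trial that is close to 1:1:2, not 1:1:1.

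The protocol therefore fixes an expected size for each arm and describes a scheme that, on its plain reading, does not deliver it. At stake are the size of the two supervised arms, the precision of aerobic versus core stability (the first research question compares all three interventions), and the number of Group 3 patients randomised alongside each supervised arm. Someone building the randomisation list from this text would have to supply a rule that the protocol does not state.

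**Working it through.** **Inputs from the Protocol.** Total 90; class size c = 10 to 12; about 10 Group 3 patients running alongside; 23 per group before dropout and 30 after; difference 0.11, SD 0.1, two-sided alpha 0.05, target power 0.85; Bonferroni correction for multiple comparisons, number not given (Data analysis).

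**Assumptions.** About 10 Group 3 patients per single class; equal numbers of aerobic and core classes; recruitment stops at 90; retention 23/30 = 76.7% in every arm.

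**1. The protocol's own totals.** 3 × 30 = 90 and 35 + 35 + 20 = 90, so these agree with each other.

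**2. Arm sizes on the plain reading.** Group 3 = 90 × 10/(c + 10), and each supervised arm = (90 − Group 3)/2.

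| Class size | Group 3 | Each supervised arm | Short of 30 by | After × 23/30 |
|---|---|---|---|---|
| 10 | 45.0 | 22.5 | 7.5 | 17.25 |
| 11 | 42.9 | 23.6 | 6.4 | 18.1 |
| 12 | 40.9 | 24.5 | 5.5 | 18.8 |

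At the mid-value c = 10.5, Group 3 = 900/20.5 = 43.9 and each supervised arm = 23.05, hence about 23/23/44.

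**3. What 30 per supervised arm would take on this scheme.** 30/12 to 30/10 = 2.5 to 3 classes per arm, so 5 to 6 pairings. That puts 50-60 patients in Group 3 and 110-120 in the trial, against 90 planned.

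**4. The reading that does give 30/30/30.** If about 10 Group 3 patients are shared by one aerobic and one core class, three cycles of 10 + 10 + 10 give 30/30/30 = 90. With classes of 12, three cycles give 36/36/30 = 102. One cycle is 30-34 patients.

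**5. Precision.** The variance factor is 1/n1 + 1/n2. For 30 v 30 it is 2/30 = 0.0667.

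- Supervised arm v all of Group 3 (c = 10): 1/22.5 + 1/45 = 0.0667, the same as 30 v 30.
- Supervised arm v concurrent Group 3 only (22.5 v 22.5): 0.0889, so the standard error ratio is √(0.0889/0.0667) = 1.155. At c = 12 (24.5 v 20.5) it is 1.16.
- Group 1 v Group 2: ratio 1.155 at c = 10 and 1.11 at c = 12.

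**6. Power at the protocol's difference and SD, after the implied loss** (two-sided t-test, noncentral t, noncentrality 1.1/√(1/n1 + 1/n2)).

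| Comparison | alpha 0.05 | Bonferroni, 3 comparisons |
|---|---|---|
| 23 v 23 (as planned) | 95% | 89% |
| Supervised v all of Group 3 | 96% | 89-90% |
| Supervised v concurrent Group 3 | 88% | 75-76% |
| Group 1 v Group 2 | 88-91% | 76-80% |

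Unadjusted power stays above 85% because the stated inputs need only 15 per group by the normal formula, or 16 by the t-test, rather than 23. That discrepancy is a separate matter.

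**The case against.** The strongest reply is that the text does not say about 10 Group 3 patients accompany every class. It states no ratio, expects several training groups at once, and labels its figures as estimates or preliminary. Shared Group 3 patients give exactly 30/30/30, and a cycle of 30-34 lies close to the 35 per year. A randomisation list can also hold arms at 30 whatever the class size. This stands to the extent that a reader might infer the scheme makes 30/30/30 impossible, and the documents do not support that. They are silent on the ratio and do not exclude sharing. Sharing is nevertheless an addition to the text: it needs aerobic and core classes to be filled together, whereas the wording is sequential and pairs Group 3 with one or the other.

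A reader might also infer that the trial is underpowered. That does not follow either. Hypothesis 1 sets supervised training against daily activity, and with all of Group 3 used it keeps the precision of 30 v 30. With concurrent controls only, unadjusted power at the stated inputs is still about 88%. It falls below 85% only after Bonferroni adjustment (about 80-81% for two comparisons and 75-76% for three), and the protocol does not fix the number of comparisons. The 23 is a weak benchmark, and the 77% retention is inferred.

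One qualification remains: the equal-precision result counts Group 3 patients randomised in the other pairing. If controls must be concurrent, the loss is real.

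**Conclusion.** The point holds as an unreconciled mismatch between the described allocation and the stated arm sizes, not as a proof that the sizes are unattainable. On the plain reading, 90 patients give 22.5-24.5 in each supervised arm and 41-45 in Group 3. About 17-19 per supervised arm remain after the implied loss, against the protocol's 23. The cost lies mainly in Group 1 versus Group 2 (standard error 11-15% larger than with 30 v 30) and in comparisons limited to concurrent controls (15-16% larger).

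This rests on the assumptions listed with the calculation, chiefly about 10 Group 3 patients per single class and a stop at 90. It should be fixed. Confidence is moderate, because the wording is ambiguous and the figures are given as estimates.

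**What to change.** Before the randomisation list is made, state the allocation ratio, say whether Group 3 patients are shared across concurrent classes, and make the arm sizes agree. Two versions are consistent with about 10 Group 3 patients at a time:

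- **Keep successive pairings at about 1:1.** Restate the expected sizes as about 23/23/44 of 90, and give the number of concurrent Group 3 patients for each supervised arm (about 20-23).
- **Keep 30/30/30.** State that patients are randomised among all three groups in the same cycle, with about 10 Group 3 patients serving one aerobic and one core class.

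Keeping successive pairings and randomising 2:1 would also give equal totals, but it is not advised. Each supervised arm would have only about 15 concurrent controls, and 1/30 + 1/15 = 0.100 is worse than the 0.089 of 22.5 v 22.5.

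Either version costs a sentence or two and a matching randomisation list, with no extra patients. The first makes the stated supervised arm sizes less favourable. The second requires aerobic and core classes to be filled in the same period. The choice needs to be made early, because the ratio cannot be restored for patients already allocated.

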Lack of reliable methods to determine what causes the pain (nonspecific back pain) makes it difficult to set a specific diagnosis. It is therefore of great importance that new methods are developed to improve the ability to the give a correct diagnose. Furthermore, the effect of different treatment on structural changes of the spine, e.g., different types of exercise, may guide how to best advice patients with different pathologies. With magnetic resonance imaging (MRI) an image of the spine can be obtained, but there is still a lack of evidence of its diagnostic benefit and knowledge if it can determine the origin of back pain. In a previous study using advanced MRI technology groups of individuals exposed to different exercise over a 3-month period demonstrated different disc patterns (22). Furthermore, new MRI techniques have demonstrated altered biodynamic properties on group level, when comparing patients with low back pain and control persons (23).

Purpose

The overall aim is to evaluate two different types of digital training interventions (aerobic, core stability) supervised by physiotherapists compared to daily physical activity in terms of clinical and patient-reported outcome (PROM) in patients with low back pain, both for short- and long-term. Furthermore, to evaluate whether new diagnostic MRI methods can identify longitudinal spine tissue changes and to analyse if there is an exercise-related difference (differences between the training groups). In addition, the ability to participate in the different exercise programs and their effect on pain in relation to baseline MRI findings will be evaluated.

Question / Hypothesis

- Do the clinical (muscle strength, conditioning, mobility, function/physical capacity) and PROM differ between patients with low back pain randomized to 3 different exercise interventions (aerobic, core stability, daily physical activity) after 6 and 12 months?

¹ the capacity of the lumbar-pelvic-hip muscle complex to control lower trunk movement and maintain stability of the vertebral column after skeletal perturbation.

² any activities that raise heart rate and make breathing somewhat harder

- Does patients' physical capacity change over time, and is there a difference between groups?
Does the training effect persist 12 months after ending the training intervention (6 months)?

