- Can new diagnostic MRI methods identify characteristic changes over time in back tissue (disc/vertebra/muscle) in patients with low back pain in the full cohort and/or after different types of exercise intervention (aerobic, core stability, daily physical activity) after 6 - 12 months?
- Are MRI-verified changes in the back detected at base line associated the ability to participate in the training interventions as well as associated with positive effect (pain relief, increased endurance and muscle strength, etc.) after participating in any of the training intervention?
- Is there a relationship between clinical changes (pain, activity level and quality of life/function) and longitudinal changes in MRI verified components of the spine tissues depending on what type of exercise intervention (aerobic, core stability, daily physical activity)?

Hypothesis 1: Supervised digital training (aerobic and/or core stability) led by physiotherapist gives better results regarding clinical and PROM compared to self-training (daily physical activity), and the effect persists after ending the intervention (6 months) in patients with low back pain.

Hypothesis 2: new MRI methods can identify exercise-related changes in the lumbar spine in patients with nonspecific low back pain after undergoing supervised physiotherapy digital training (aerobic and/or core stability).

Hypothesis 3: there is a relationship between identified changes in low back tissues and the effect of different types of exercise interventions in patients with low back pain.

Method & Materials

Patients seeking primary health care (primarily Vänersborg/Trollhättan/Uddevalla, Sweden) for lower back pain will be asked to participate. Inclusion criteria: low back pain > 3 months, 18-50 years, have access to computer/tablet/mobile

Exclusion criteria:

- Inadequate Swedish as the language is an obstacle to be able to fully understand written and oral information regarding the project and to follow training instructions
- Other ongoing treatment/exercise for their low back pain
- Age > 50 years
- Patients with radiating leg pain and other neurological symptoms
- Previous back/neck surgery
- Pregnancy
- Diagnosed systematic diseases engaging the spine as rheumatoid arthritis, ankylosing spondylitis
- Factors that prevent an MRI examination, such as claustrophobia, metal implants, etc.

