All patients (groups 1-3) will be able to continuously book a video appointment with the physiotherapist responsible for the training during the whole intervention period.

Any problems that cannot be solved during video consultation or at a follow-up examination will be referred back to the attending physician.

MRI scan

All included patients will be examined with MRI including T1- and T2-weighted sequences and functional imaging methods (such as DTI, DIXON and T2 mapping).

Data collection

Training intervention

³ a chemical shift imaging method

⁴ a magnetic resonance imaging technique used to calculate the T2 times of a certain tissue and display them voxel-wise on a parametric map.

Clinical examination of the low back will be performed according to standard routine (baseline – 6 months – 12 months) by an experienced physiotherapist. The examination will also include muscle strength tests and assessment of physical capacity.

At the same occasion, the patient will undergo MRI examination according to the protocol above. Responsible for the development of specific imaging methods and training of staff at the Imaging and Function Department is an experienced MRI physicist.

All clinical data will be recorded in the patient's medical record. All MRI scans will be archived as a medical record according to the hospital's regulations.

The patients will answer several questionnaires at the base line, 3 – 6 – 12 months. The questionnaires are registered in a web-based Survey & Reporting program (<https://webropol.se/>). The patients will receive mail or SMS with information when and how to answer the questionnaires.

The questionnaires include demographic data (based on questions included in SweSpine (<https://www.swespine.se/>), physical activity (<https://www.socialstyrelsen.se/>), as well as established and validated questionnaires regarding low back pain such as VAS (24), Oswestry Low Back Pain Disability Questionnaire (25), TAMPA scale of kinesiophobia (26), Hospital Anxiety and Depression Scale (HAD) (27), Swedish Version of the General Self-Efficacy Scale (28) and EQ-5D-5L (29)

Analysis of MRI examination

Conventional radiological categorization schemes (identification of high intensity zones = HIZ in the intervertebral discs and Modic changes in the vertebrae), as well as advanced analysis methods (e.g. histogram analysis, shape/texture analysis and regional analysis) will be used for detailed characterization of the vertebrae/disc/muscle.

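### The test is left to an undefined data-quality criterion and no outcome, time point or contrast is designated to decide Hypothesis 1; a prespecified baseline-adjusted comparison with Group 3 would close both gaps cheaply

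*Protocol*

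**What the plan says.** - **Choice of test.** Data analysis: "Comparisons between and within groups will be conducted using either parametric or non-parametric statistical methods depending on data quality". The criterion is not defined. Tests are two-sided at 0.05, and "Bonferroni correction will be performed when multiple comparisons are done"; the family to be corrected is not given.
- **Hypothesis 1.** "Supervised digital training (aerobic and/or core stability) led by physiotherapist gives better results regarding clinical and PROM compared to self-training (daily physical activity". This fixes the comparator. It leaves the contrast open (either arm, both, or the two pooled) and takes all clinical and patient-reported results as the outcome.
- **Time points.** The first research question asks about 6 and 12 months without ranking them. Under Data collection, "The patients will answer several questionnaires at the base line" and again at 3, 6 and 12 months. Baseline VAS is therefore available.
- **Sizing outcome.** The training sample size is "based on a p-value 0.05, power 0.85, SD 0.1 and a minimal clinical change in Visual Analog Scale (VAS)/pain 0.11", giving 23 per group, with 30 per group planned. No visit is attached to it.
- **Randomisation.** Under Training intervention, patients are first randomised between Groups 1 and 3, and later between Groups 2 and 3.
- **Persistence.** The Question / Hypothesis section asks about persistence 12 months after a 6-month training period ends. Data collection stops at 12 months.

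**The concern.** The protocol itself makes the method depend on the data through a criterion that nobody can apply in advance. A later analysis plan that followed the sentence would inherit that dependence. With outcome, visit, contrast and form of comparison (follow-up value, change, or baseline-adjusted value) also open, the analysis taken as the answer to Hypothesis 1 could be settled once results are visible. The stated Bonferroni rule corrects the comparisons that are made and reported. It does not correct for analyses tried and set aside.

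There is also an efficiency cost. Baseline values are collected but nothing commits the analysis to using them. An unadjusted comparison is valid, but its interval is wider than it need be.

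**Working it through.** **Inputs from the protocol:** SD 0.1, VAS difference 0.11 (standardised difference 0.11/0.1 = 1.1), two-sided 0.05, power 0.85, 23 per group. **Assumed, because the protocol does not give it:** correlation r between baseline and follow-up VAS of 0.3, 0.5 or 0.7.

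**1. The plan's own figure.** Per-group n = 2(1.960 + 1.036)² × (0.1/0.11)² = 14.8, so 15, or 16 with the exact t-test. The stated 23 is not reproduced. At 23 per group the exact t-test has power 0.95. This is a separate matter; it means only that the trial is not short of patients on its stated inputs.

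**2. Error from the open choice.** Simulated under no difference, 23 per group, nominal 5%, r from 0.3 to 0.7 where baseline is involved:

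| Procedure | False-positive rate |
|---|---|
| Normality pre-test, then t or rank test | 4.5% to 5.2% |
| Smaller p of t and rank test, follow-up value | about 6% (up to 6.7% on strongly skewed data) |
| Smaller p of t-tests on follow-up and on change | 8.7% to 9.4% |
| Smallest p of all four | 10.2% to 10.8% (normal); up to 11.5% (skewed) |
| ANCOVA fixed in advance | 4.6% to 5.2% (normal and skewed) |

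At a Bonferroni level of 2.5% the smallest of four gives 5.0% to 5.5%, again about double. Because ANCOVA fixed in advance holds its level on skewed data too, a data-driven switch is not needed to protect the error rate.

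**3. What is undesignated.** Six named questionnaires × two visits (6 and 12 months) × three readings of the contrast = 36 candidate tests for Hypothesis 1, before any clinical test is counted. If all were counted, the Bonferroni level would be 0.05/36 = 0.0014. If only Groups 1 v 3 and 2 v 3 on one outcome at one visit were counted, it would be 0.05/2 = 0.025. The protocol does not say which.

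**4. Precision of a baseline-adjusted comparison.** The variance relative to a follow-up comparison is 1 − r² = 0.91, 0.75 or 0.51. The 97.5% half-width is t × 0.1 × √(1 − r²) × √(2/23), with √(2/23) = 0.2949:

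- Unadjusted: 2.321 × 0.1 × 0.2949 = 0.068
- r = 0.3: 2.323 × 0.1 × 0.954 × 0.2949 = 0.065
- r = 0.5: 2.323 × 0.1 × 0.866 × 0.2949 = 0.059
- r = 0.7: 2.323 × 0.1 × 0.714 × 0.2949 = 0.049

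Power at 0.025 is 0.92 unadjusted and 0.94, 0.97 or above 0.99 adjusted. The gain is mainly in interval width.

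**5. Effect of the two-stage randomisation.** Step 4 lets every Group 3 patient serve both comparisons. Group 1 is recruited only against first-stage Group 3 patients, and Group 2 only against second-stage ones. A phase term in an additive model therefore gives the same contrast as restricting to concurrent controls. If Group 3 splits evenly (assumed), about 12 of its 23 serve one comparison:

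- Variance factor: (1/23 + 1/12)/(2/23) = 1.46
- Net of baseline adjustment at r = 0.5: 1.458 × 0.75 = 1.09 times the unadjusted, unphased variance
- Break-even: r = √(1 − 1/1.458) = 0.56

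Against a concurrent-only comparison without baseline, adjustment still removes the fraction r².

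**6. Persistence.** Twelve months after a 6-month training period is month 6 + 12 = 18. The last listed visit is month 12, which is 6 months after training ends.

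**The case against.** Much of this is ordinary analysis-plan content. A distribution criterion, the choice between change score and ANCOVA, and sensitivity tests are commonly left to a plan that is not shown here. The sentence covers outcomes of very different kinds, from VAS to Modic types, so allowing both families of test is normal drafting, and it does not exclude ANCOVA. This stands in part: the missing criterion alone would not justify a comment. What remains is that the protocol states a data-dependent rule, and that the outcome and visit deciding the main hypothesis belong in the protocol.

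Three stronger readings are tempting, and the document does not support them:

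- **That the quoted rule doubles the error rate.** It does not. The 10% to 11% comes mostly from choosing between follow-up and change scores, which the sentence does not mention, and it needs an analyst who reports the best of four results. Likewise, 36 uncorrected and independent tests would give 1 − 0.95³⁶ = 0.84, but the protocol promises Bonferroni and the outcomes are unlikely to be independent.
- **That no between-group comparison is specified.** Comparator, visits and sizing outcome are all named. What is missing is the designation.
- **That within-group tests are being misused.** Nothing says they will support Hypothesis 1. They answer other stated questions: whether "physical capacity change over time, and is there a difference between groups", and the MRI sizing "regarding the T2 value between the three occasions".

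It is also fair to object that the precision gain in step 4 may not survive the design. Step 5 confirms that it can be cancelled, so it should not be promised.

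**Conclusion.** The point holds in a limited form. The data-quality criterion is undefined, and no outcome, visit or contrast is designated for Hypothesis 1. The test-choice rule by itself is nearly harmless (about 6% against 5%). The 10% to 11% figure is a worst case with follow-up or change score also chosen after the fact, at 23 per group and r of 0.3 to 0.7. The open outcome, visit and contrast matter more, since the correction level could lie anywhere between 0.025 and about 0.0014 depending on what is counted.

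Baseline adjustment narrows the 97.5% interval from 0.068 to between 0.065 and 0.049, on the protocol's SD and an assumed r. Once concurrent controls are respected, a net gain over the unadjusted, unphased comparison appears only above r of about 0.56, if Group 3 splits evenly. This should be changed because it is cheap, not because the trial is invalid without it.

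**What to change.** 1. For Hypothesis 1, replace the data-quality clause by a prespecified baseline-adjusted between-group comparison: ANCOVA, or a mixed model over the follow-up visits with group, time, group-by-time and baseline value.
2. Designate VAS pain at 6 months as deciding Hypothesis 1. Report Groups 1 v 3 and 2 v 3, each tested at 0.025 with a 97.5% confidence interval, so that test and interval match.
3. Keep a rank test as a fixed sensitivity analysis.
4. Compare each arm with its concurrent Group 3 patients or include randomisation phase, and say that this can offset the precision gain.
5. Reconcile the persistence question (12 months after training ends) with the visit schedule (to 12 months only) before fixing that analysis.

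The cost is a few sentences. The protocol already names SPSS, which fits these models, and no new data or patients are needed. One degree of freedom goes to baseline, and a rule is needed for patients without a baseline value. Respecting the two stages multiplies the variance by about 1.46 under an even split of Group 3.
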